1.2 Secondary objectives

Secondary objectives of the study are:

- 1. To determine the *EGFR* mutation frequency (including mutation subtypes) in patients with advanced NSCLC (aNSCLC) of adenocarcinoma and non-adenocarcinoma histologies.
- 2. To describe first line therapy choice following *EGFR* mutation testing.
- 3. To describe second line therapy choice following discontinuation of first line treatment for patients confirmed as *EGFR* mutation positive via tissue/cytology.
- 4. To summarise *EGFR* mutation testing practices in terms of methods, sample types, success rate, mutation detection rate, testing turnaround time and reasons for not testing.
- 5. To determine the correlation between *EGFR* mutation status from tumour and demographic data and disease status.
- 6. To determine the correlation between *EGFR* mutation status derived from plasma (blood) and demographic data and disease status.

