3. SELECTION OF SUBJECT POPULATION

- Patients with locally advanced (stage IIIA/B) or metastatic NSCLC who are newly diagnosed, have not received any local or systemic chemotherapy. Locally advanced patients should not be eligible for curative treatment (including surgery and chemoradiotherapy). The tumour samples of these patients are planned to undergo EGFR mutation testing, or have had an EGFR mutation test within 2 months of screening, or
- Patients who have newly diagnosed locally advanced (stage IIIA/B) NSCLC who are not eligible for curative treatment (including surgery and chemoradiotherapy) or metastatic NSCLC and have not received systemic chemotherapy. Previous or planned palliative radiotherapy is allowed. The tumour samples of these patients are planned to undergo EGFR mutation testing, or have had an EGFR mutation test within 4 months of screening, or
- Patients who have had surgical resection with or without adjuvant chemotherapy and have experienced recurrent disease. In this case if a new/contemporary biopsy is available, it should be used for *EGFR* mutation testing. If the only sample available is a historical diagnostic/resected sample, then this may be used for *EGFR* mutation testing (no time- limit from screening).

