12. STATISTICAL METHODS AND SAMPLE SIZE DETERMINATION

12.1 Description of outcome variables in relation to objectives and hypotheses

No formal statistical hypothesis tests will be made in this study.

The relationship between the objectives and outcome variables is described in the table below.

Objectives	Outcome variables	
Primary objectives		
To determine the level of concordance between EGFR mutation status obtained via tissue/ cytology and blood (plasma) based testing.	Concordance rate, sensitivity, specificity, positive and negative predictive values between sample types.	
Secondary objectives		
- To determine the EGFR mutation frequency (including mutation subtypes) in patients with advanced NSCLC (aNSCLC) of adenocarcinoma and non- adenocarcinoma histologies.	EGFR mutation frequency overall and by adenocarcinoma and non-adenocarcinoma histologies and by country/region.	
- To describe first line therapy choice following EGFR mutation testing.	% first line treatment choices by mutation status and by country/region and mutation subtype.	
 To describe second line therapy choice following discontinuation of first line treatment for patients confirmed as EGFR mutation positive via tissue/cytology. 	% patients on 2 nd line treatment, treatment sequence, % second line treatment choices by country/region and mutation subtype for EGFR mutation positive for tumour.	
 To summarise EGFR mutation testing practices in terms of methods, sample types, success rate, mutation detection rate, testing turnaround time and reasons 	EGFR mutation test method, sample type, success rate, mutation detection rate, testing turnaround time and reasons for testing not being performed summarised overall and by	

Table 4: Study objectives and outcome variables

for not testing.

- To determine the correlation between *EGFR* mutation status from tumour and demographic data and disease status.
- To determine the correlation between EGFR mutation status derived from plasma (blood) and demographic data and disease status

country/region.

Correlation of mutation status from tumour with demographic characteristics and disease status data.

Correlation of mutation status from plasma (blood) with demographic characteristics and disease status data.

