13.2 Evaluable Population

The Evaluable Population consists of all enrolled patients with all non-missing or unknown:

- Tumour sample *EGFR* mutation test status.
- Tumour sample *EGFR* mutation test sub-type.
- Plasma *EGFR* mutation test status.
- Plasma *EGFR* mutation test sub-type.

Unless otherwise specified all summaries will be based on the Evaluable Population.

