14.2 Secondary Objectives

EGFR Mutation Frequency

The *EGFR* mutation frequency from the tumour sample in the evaluable population will be summarised overall and by country/region by adenocarcinoma and non-adenocarcinoma histologies.

First line treatment choice

 1^{st} line treatment choice following *EGFR* mutation testing will be summarised descriptively for the overall evaluable population by *EGFR* mutation status, *EGFR* mutation subtype and

by country/region.

Second line treatment choice

The percentage of patients on 2^{nd} line treatment, including treatment choice following discontinuation of first line treatment for patients confirmed as *EGFR* mutation positive via tissue/cytology will be summarised descriptively for the evaluable EGFR mutation positive population by *EGFR* mutation status, *EGFR* mutation subtype and by country/region. Treatment sequence i.e. 1^{st} line treatment choice and 2^{nd} line treatment choice will be summarised descriptively.

Summaries of EGFR mutation testing practices

The testing methodology, sample type and availability, testing turnaround time, testing success rate and mutation detection rate will be summarised using appropriate descriptive statistics for evaluable population. The reasons for testing not being performed will be listed.

Correlation between EGFR mutation status from tumour sample and demographic characteristics and disease status

The patient characteristics of the enrolled population will be compared to the characteristics of the evaluable population in order using summary statistics to understand any relationship between all aNSCLC patients and those whose samples undergo *EGFR* mutation testing.

The correlation between *EGFR* mutation status and both demographic characteristics and disease status will be analysed using a multivariate logistic regression model, constructed for the evaluable population to model *EGFR* tumour mutation status at baseline (*EGFR* mutation positive versus *EGFR* mutation negative from tumour sample) and key demographic characteristics such as histology (adenocarcinoma versus non-adenocarcinoma), smoking status (never- versus eversmoker) gender (female versus male), age (≤ 65 versus 65+) and WHO performance score (PS; 0-1, 2) and key disease status characteristics (time since diagnosis, disease stage at progression and number of organs with metastasis).

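### Reasons for not testing fall by default on the Evaluable Population, which contains no untested patient, so the summary would be empty as specified

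*Protocol*

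**What the plan says.** Secondary objective 4 (Protocol Section 1.2) covers testing practices, including "success rate, mutation detection rate, testing turnaround time and reasons for not testing". Section 7.2 collects the reasons as a study variable.

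Two places describe the output. Table 4 in Section 12.1 has "reasons for testing not being performed summarised overall and by" country/region. Section 14.2, under its paragraph on testing practices, says "The reasons for testing not being performed will be listed". Neither names an analysis set for this item. The sentence just before it in Section 14.2 does name one for the other testing variables: "testing success rate and mutation detection rate will be summarised using appropriate descriptive statistics for evaluable population".

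Section 13.2 supplies the default: "Unless otherwise specified all summaries will be based on the Evaluable Population". It defines that set as follows: "The Evaluable Population consists of all enrolled patients with all non-missing or unknown", and then lists tumour status, tumour subtype, plasma status and plasma subtype. Section 13.1 defines the Enrolled Population as everyone who signs consent.

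On entry, Section 3 sets this condition for newly diagnosed patients who may have had palliative radiotherapy: "The tumour samples of these patients are planned to undergo EGFR mutation testing, or have had an EGFR mutation test within 4 months of screening". The other newly diagnosed group has the same condition with a 2-month window. The recurrent-disease group has no such condition.

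**The concern.** A summary of why patients were not tested needs a set that can contain untested patients. The default set is built from patients who have results on both samples, so it removes exactly the patients whom the item is about. If the rule is applied as written, one named component of a secondary objective is reported as an empty table. A reader of the report could take that as a finding that hardly anyone goes untested, when it only reflects the choice of set.

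A second, narrower issue is what the item can mean even in the right set. Newly diagnosed patients are selected on having a test planned or done, so for them the study can observe why an intended test did not happen, but not why a clinician never intended one.

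**Working it through.** The plan states no figure on this point, so the check is one of definitions.

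**Step 1. Which set applies?** Table 4 calls the output a summary and names no set. Section 14.2 calls it a listing and names no set. The Section 13.2 default covers all summaries with no set specified. The Table 4 output is therefore based on the Evaluable Population.

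**Step 2. Can that set contain an untested patient?** The definition's wording (non-missing or unknown) is ambiguous. Read literally, it could admit patients with unknown status. But Section 14.1 computes concordance, sensitivity, specificity and predictive values in this set, and these need a positive or negative result on both samples. Section 7.2 defines unknown as neither. The workable reading is neither missing nor unknown. On that reading:

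- evaluable patients with a reason for not being tested = 0, whatever the enrolment.

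**Step 3. Does the Enrolled Population contain untested patients?** It can.

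- Section 13.1 requires consent only.
- Section 3.2 requires provision of a tumour sample, not a result.
- Section 3 accepts a test that is merely planned.
- Section 8.1.1 allows material to be excluded as inappropriate, insufficient or poorly preserved.
- Section 8.1.2 makes testing conditional on suitable material.
- Section 14.2 itself contrasts enrolled patients with those whose samples are tested.

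**Step 4. How many might there be?** The protocol gives no rate of planned tests not done. With planned enrolment of 1300 (1000 Europe + 300 Japan, Section 2.1) and an assumed share:

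| Assumed share untested | Enrolled, untested | Evaluable, untested |
|---|---|---|
| 1% | 1300 × 0.01 = 13 | 0 |
| 2% | 1300 × 0.02 = 26 | 0 |
| 5% | 1300 × 0.05 = 65 | 0 |
| 10% | 1300 × 0.10 = 130 | 0 |

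Even at 1%, treating patients as independent, the chance of no untested patient among 1300 is 0.99^1300, about 2 in a million. An enrolled-set summary would have content across this range.

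**Step 5. Cross-check on a neighbouring item.** Section 7.2 defines the testing success rate as tests giving a positive or negative result divided by tests requested. Section 14.2 assigns it expressly to the Evaluable Population. Counting one tumour test per patient, numerator and denominator are equal there, so the rate is 100% by construction. The same set is unsuitable for both items.

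**The case against.** The strongest reply is that the Section 14.2 sentence describes a listing, stands apart from the sentence that names the evaluable set, and uses a different verb. The Section 13.2 default speaks of summaries. A listing of reasons is naturally read as covering those who were not tested, and the set for a listing is often left to the SAP, which is not shown. This is fair as far as Section 14.2 goes, and it means an empty output is not inevitable in practice. It does not dispose of Table 4, which calls for a summary and so falls under the default. The protocol is not silent here: it fixes a rule, and the rule gives the wrong set.

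It can also be said that the item is one descriptive component of one of six secondary objectives, in a study without hypothesis tests. That stands and limits the weight of the point.

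A reader might go further and infer that untested patients cannot enter the study at all, so that this part of objective 4 cannot be answered. The documents do not support that: entry needs consent, a sample and, for newly diagnosed patients, a test planned or done, and a planned test may not take place. Nor does the planned-or-done condition apply to recurrent disease. A reader might also infer that the study claims to measure access to testing. Access appears only in the rationale; no objective or Table 4 outcome measures it.

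**Conclusion.** The point holds in this form: under Table 4 and the Section 13.2 default, the reasons for not testing are summarised in a set with 0 untested patients, and the output is empty by construction. This rests on reading the Evaluable definition as excluding both missing and unknown results, the only reading that serves the primary analysis.

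The information is recoverable from the Enrolled Population. The 13 to 130 patients rest on an assumed 1% to 10% share and only illustrate scale. What the enrolled set can show is why a test was not carried out in patients who entered. For the two newly diagnosed groups it cannot show why testing is never requested.

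The primary analysis is unaffected. The correction is worth making because a stated objective would otherwise be reported from the wrong set.

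**What to change.** 1. In Section 14.2 and Table 4, state that reasons for a tumour EGFR test not being performed are summarised, overall and by country/region, for all enrolled patients without a performed tumour test, with all enrolled patients as the denominator.
2. Make the two places agree on the form of output. If a patient listing is wanted as well, say so and give it the same set.
3. Reword this component of objective 4 (now "testing turnaround time and reasons for not testing") as reasons why an EGFR test was not carried out in enrolled patients. Add a sentence that it does not estimate why clinicians do not request testing in routine practice, because newly diagnosed patients enter only with a tumour test planned or already done.

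While editing, it would be sensible to reword the Evaluable definition so that it plainly excludes unknown results, and to move the testing success rate to the enrolled set for the same reason.

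The cost is wording in objective 4, Table 4 and Section 14.2. The reasons are already collected under Section 7.2, so no new data are needed. The drawback is a narrower claim.

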Non-Interventional Study (NIS) ProtocolNIS Name/CodeD7913C00070Edition NumberFinal 3.0Date

A diagnostic Study of European and Japanese advanced NSCLC patients to evaluate suitable sample types for EGFR testing: The ASSESS Study

Sponsor:

AstraZeneca AB, [name]

A diagnostic Study of European and Japanese advanced NSCLC patients to evaluate suitable sample types for EGFR testing: The ASSESS Study

Medicinal Products (type, dose, mode of administration) and concomitant medication

The assignment of a subject to a particular therapeutic strategy is not decided in advance by a protocol but falls within current practice and marketing authorisation.

Study Rationale

This study will be conducted in Japan and Europe and will assess the concordance of *EGFR* mutation status derived from tumour samples and blood based circulating free DNA. The data generated will inform the use of less-invasive sample types in diagnostic practice. The study also aims to assess the current status of *EGFR* mutation testing across Japan and Europe and gaps in currently available data including *EGFR* mutation frequency in particular populations and demographic subgroups, *EGFR* mutation frequency in histological subtypes of NSCLC, *EGFR* mutation test process and methodology, utility of multiple sample types in the assessment of *EGFR* mutation status, and impact of *EGFR* mutation testing process, ensuring that patients have access to testing and are treated appropriately on the basis of the molecular features of their disease.

Study Objectives

(a) Primary objective

To determine the level of concordance between *EGFR* mutation status obtained via tissue/cytology and blood (plasma) based testing.

- (b) Secondary objectives
- 1. To determine the *EGFR* mutation frequency (including mutation subtypes) in patients with advanced NSCLC (aNSCLC) of adenocarcinoma and non-adenocarcinoma histologies.
- 2. To describe first line therapy choice following *EGFR* mutation testing.
- 3. To describe second line therapy choice following discontinuation of first line treatment for patients confirmed as *EGFR* mutation positive via tissue/cytology.
- 4. To summarise *EGFR* mutation testing practices in terms of methods, sample types, success rate, mutation detection rate, testing turnaround time and reasons for not testing.
- 5. To determine the correlation between *EGFR* mutation status from tumour and demographic data and disease status.

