2.2.2 EGFR mutation assessment of cfDNA from Blood (plasma) Samples

All screened patients will be asked to provide a mandatory blood (plasma) sample. These samples will be used for the extraction of cfDNA and determination of *EGFR* mutation status a nominated central laboratory.

All patients will be required to provide the following:

• 1 x 10 mL blood, from which the plasma will be isolated.

Samples will be collected, labelled, stored and shipped as detailed in the laboratory manual.

Residual material may be used for optional exploratory biomarker research if the patient consents to this research.

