- Exon 20:
 - o T790M
 - o insertions
 - o other
- Exon 21:
 - o S768I
 - o L858R
 - o L861Q
 - o Other

The following outcome variables will be calculated in order to fulfil the secondary objectives of the study:

EGFR Testing Overall Endpoints

- Test failure rate, calculated as, tests not performed successfully providing an "unknown" or "fail" test result/ number of tests requested
- Mutation detection rate, calculated as performed successfully providing a "positive" mutation result / total number of successful tests providing a mutation result
- Testing success rate, calculated as, tests performed successfully providing a mutation result (positive/negative) / total number of tests requested

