14. METHOD OF STATISTICAL ANALYSIS

Descriptive summary of patient demographics and disease characteristics will be presented for all enrolled population and the evaluable population.

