Correlation between *EGFR* mutation status derived from plasma sample and demographic characteristics and disease status

The *EGFR* mutation status from plasma sample and demographic and disease characteristics will be summarised for the evaluable population with available samples. This summary will be compared with summaries of the *EGFR* mutation status from tumour samples within the same demographic and disease status characteristics to understand any patterns of differences in the mutation detection rate in the plasma sample within key patient sub-groups.

The correlation between *EGFR* mutation status from plasma sample and both demographic characteristics and disease status will be analysed using a multivariate logistic regression model, constructed for the evaluable population to model *EGFR* tumour mutation status at baseline (*EGFR* mutation positive versus *EGFR* mutation negative from tumour sample) and key demographic characteristics such as histology (adenocarcinoma versus non-adenocarcinoma), smoking status (never- versus eversmoker) gender (female versus male), age (≤ 65 versus 65+) and WHO performance score (PS; 0-1, 2) and key disease status characteristics (time since diagnosis, disease stage at progression and number of organs with metastasis).

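### Objective 6 and the plasma testing rates need only a plasma result, but the protocol restricts them to patients whose tumour result is also known

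*Protocol*

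**What the plan says.** Objective 6 (Protocol section 1.2) relates plasma EGFR status to demographic and disease data. For its analysis, section 14.2 states that "mutation status from plasma sample and demographic and disease characteristics will be summarised for the evaluable population with available samples", and it builds the accompanying logistic regression in the same population.

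Section 13.2 defines that population: "The Evaluable Population consists of all enrolled patients with all non-missing or unknown", followed by four items (tumour status, tumour sub-type, plasma status, plasma sub-type). It also sets the default: "Unless otherwise specified all summaries will be based on the Evaluable Population".

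For testing practices (objective 4), section 14.2 says that "testing success rate and mutation detection rate will be summarised using appropriate descriptive statistics for evaluable population". Section 7.2 defines success and failure rates with the number of tests requested as denominator, and detection rate with the number of successful tests as denominator.

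The Enrolled Population is used only for patient characteristics. Section 14 states: "Descriptive summary of patient demographics and disease characteristics will be presented for all enrolled population and the evaluable population". Section 14.2 adds a comparison of the two sets on those characteristics.

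Plasma collection does not depend on the tumour result. Section 2.2.2 says: "All screened patients will be asked to provide a mandatory blood (plasma) sample".

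**The concern.** A known tumour result is needed to compute concordance, sensitivity, specificity and predictive values. It is not needed to describe plasma status by patient characteristics, to model plasma status, or to say how often the plasma test gives a result. Requiring it there has three effects.

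- Plasma results from patients with an unknown tumour result are collected but not analysed.
- Objective 6 is answered in patients selected on the success of a different test. Section 8.1.1 lists insufficient tumour sample and poor fixation among the reasons for excluding material. Failure may therefore be related to disease characteristics, and the protocol does not show that it is random.
- The plasma success rate cannot do its job, because plasma failures are removed before it is computed.

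The Study Rationale says: "The data generated will inform the use of less-invasive sample types in diagnostic practice". It also lists the utility of multiple sample types among the gaps to be assessed. How often plasma yields a result, including when the tumour test did not, bears on that aim.

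**Working it through.** **1. Which set does each plasma analysis use?**

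| Analysis | Results it needs | Set named in the protocol |
|---|---|---|
| Concordance and related measures (14.1) | tumour and plasma | Evaluable |
| Plasma summary by characteristics (14.2, objective 6) | plasma | Evaluable |
| Tumour-versus-plasma comparison within subgroups (14.2, objective 6) | tumour and plasma | Evaluable |
| Regression for objective 6 (14.2) | plasma | Evaluable; the outcome named is tumour status |
| Testing success and detection rates (14.2, objective 4), as applied to plasma | plasma | Evaluable |
| Patient characteristics (14 and 14.2) | none | Enrolled and Evaluable |

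The Evaluable Population requires tumour and plasma results together. A patient with known plasma and unknown tumour status fails the tumour condition and is in none of the sets used for a plasma result. The number of such patients contributing to any planned plasma analysis is zero.

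**2. Plasma success rate.** By section 7.2, success = tests giving positive or negative / tests requested. Every member of the Evaluable Population has a known plasma status, so numerator and denominator coincide and the rate is about 100% whatever the true performance. Only failed first attempts later repeated successfully could lower it, if attempts were counted separately.

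**3. The protocol's own figure.** Section 15 gives a 95% CI of 40% to 60% for a sensitivity of 50% with 100 positives. The exact interval for 50/100 is 39.8% to 60.2%, so it reproduces. Europe gives 1000 x 0.10 = 100 positives; Japan gives 300 x 0.30 = 90. These figures serve only as inputs below.

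**4. Size.** No tumour-test failure rate is given, so u = 2%, 5% and 10% are assumptions, with every such patient taken to have a valid plasma result.

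- Patients left out = 1300 x u.
- Expected plasma positives among them = u x (1000 x 0.10 x 0.5 + 300 x 0.30 x 0.5) = u x (50 + 45) = 95u. This uses the protocol's frequencies and sensitivity, assumes that they hold in tumour-unknown patients, and assumes no false positives.

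| u | Left out: Europe + Japan = total | Expected plasma positives | Exact 95% CI for positive rate (rounded count) |
|---|---|---|---|
| 2% | 20 + 6 = 26 | 1.9 | 0.9% to 25.1% (2/26) |
| 5% | 50 + 15 = 65 | 4.75 | 2.5% to 17.0% (5/65) |
| 10% | 100 + 30 = 130 | 9.5 | 3.8% to 13.7% (10/130) |

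**5. Precision of a plasma call rate in tumour-unknown patients.** At u = 5% and an assumed call rate near 95%, the pooled result 62/65 has an exact 95% CI of 87.1% to 99.0%. For Japan alone, 14/15 gives 68.1% to 99.8%, and 2 positives in 15 gives 1.7% to 40.5%.

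**The case against.** **The paired set has a purpose in section 14.2.** The objective 6 text goes on to compare plasma with tumour summaries within the same subgroups. Using different patients for the two would mix population differences with assay differences. This stands for the comparison. It does not justify the same restriction on the standalone plasma summary or on a plasma-status model.

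**The population wording is uncertain.** Section 13.2 could be read literally as admitting unknown results, and the reference to available samples in section 14.2 is redundant if plasma results are already required. But concordance cannot be computed with unknown results, so the intended reading excludes them, and the available-samples phrase can only narrow the set.

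**The SAP could add analyses.** It could, and the data are collected in any case. The point here is not an omitted detail, however: the protocol names the set for these analyses.

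**The numbers may be small.** This stands. The loss could be a few percent, objective 6 estimates might move little, and per-region tables could be close to uninformative, above all in Japan.

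**A stronger reading.** A reader might infer that the study cannot say what blood testing yields where it is most needed. The documents do not support that. Plasma yield after tumour-test failure is not among the stated objectives, and the protocol nowhere identifies those patients as having the greatest need. Section 3.2 requires a confirmed diagnosis and a tissue or cytology sample, so patients with no tumour material to give are not enrolled at all, and no re-analysis would recover them. What can be said is that the planned analyses do not report these plasma results, although the data to do so will exist.

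**Conclusion.** The point holds as a mis-specified analysis population for secondary objective 6 and for the plasma part of objective 4. By the protocol's own rules, valid plasma results without a known tumour result enter no plasma analysis, objective 6 is conditioned on tumour-test success, and plasma success is about 100% by construction, in conflict with the section 7.2 denominator. These conclusions follow from the definitions and need no assumed figure.

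The number of patients affected does rest on assumption: 26 to 130 of 1300 for an assumed failure rate of 2% to 10%. The direction and size of any bias in objective 6 cannot be derived from the document. The change should be made because it is cheap and corrects two secondary objectives; it does not touch the primary analysis.

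**What to change.** - **Section 14.2, objective 6:** run the standalone plasma summary in all eligible enrolled patients with a known plasma status. Run the regression in the same set with plasma status as its outcome. The text now names tumour status, and tumour-unknown patients could not enter that model.
- **Keep the paired Evaluable Population** for concordance (section 14.1) and for the tumour-versus-plasma comparison within subgroups.
- **Section 14.2, testing practices:** compute plasma success over all plasma tests requested and plasma detection over all successful plasma tests, as section 7.2 defines them.
- **Section 13.2:** reword the definition so that it plainly excludes missing and unknown results.
- **Add one descriptive 3x3 table** of tumour result by plasma result (positive, negative, unknown), overall and by region. Give plasma call and positive rates among tumour-unknown patients with exact 95% CIs.

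The cost is a few changes of wording and one small table, with no new samples or visits. The drawback is wide intervals in the tumour-unknown group, especially in Japan, if few tumour tests fail. The overall table should therefore carry the weight and the regional ones be read as description.

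### The plasma logistic regression in Section 14.2 names tumour mutation status as its outcome, so secondary objective 6 has no valid multivariable analysis

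*Protocol*

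**What the plan says.** Protocol Section 1.2 gives secondary objective 6 as: "To determine the correlation between *EGFR* mutation status derived from plasma (blood) and demographic data and disease status". Table 4 in Section 12.1 pairs it with this outcome variable: "Correlation of mutation status from plasma (blood) with demographic characteristics and disease status data".

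The plasma subsection of Section 14.2 plans two things for this objective.

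- **A descriptive part.** EGFR "mutation status from plasma sample and demographic and disease characteristics will be summarised for the evaluable population with available samples". The result is set beside the tumour summaries in the same categories "to understand any patterns of differences in the mutation detection rate in the plasma sample within key patient sub-groups".
- **A regression.** The sentence opens with plasma: EGFR "mutation status from plasma sample and both demographic characteristics and disease status will be analysed using a multivariate logistic regression model". It then says the model is constructed for the evaluable population "to model *EGFR* tumour mutation status at baseline (*EGFR* mutation positive versus *EGFR* mutation negative from tumour sample".

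The tumour subsection just before it, which serves objective 5, defines its own regression in the same terms.

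**The concern.** The regression sentence contradicts itself. It announces an analysis of plasma status and then fixes a tumour result as the dependent variable. The definition names the tumour twice, once for the status and once for the sample, so this is not one ambiguous word. Plasma status is not among the listed covariates either, so the model as specified contains no plasma result at all.

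Two things are at stake. First, the multivariable answer to objective 6 is lost. Second, a report that followed the text literally would show the same odds ratios under a tumour heading and a plasma heading. A reader could take that as evidence that the two sample types share the same correlates. Whether plasma can stand in for tumour tissue is the question the study was set up to answer (Section 1.1).

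**Working it through.** **Step 1: the two specifications side by side (Section 14.2).**

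| Element | Tumour regression (objective 5) | Plasma regression (objective 6) |
|---|---|---|
| Subsection heading and opening words | Tumour status (the opening says only EGFR status) | Plasma status |
| Modelled outcome | Tumour status, positive vs negative in the tumour sample | The same |
| Analysis set | Evaluable Population | The same |
| Demographic covariates | Histology, smoking, gender, age group, performance score | The same |
| Disease covariates | Time since diagnosis, stage at progression, number of organs with metastasis | The same |

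For the last row, both subsections contain "key disease status characteristics (time since diagnosis, disease stage at progression and number of organs with metastasis".

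**Step 2: are the patients the same?** Section 13.2 begins "The Evaluable Population consists of all enrolled patients with all non-missing or unknown" and then lists tumour and plasma status and subtype. I read this as requiring a known result from both sample types. Both regressions use this set. With the same patients, outcome and eight covariates, the two fits are identical.

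**Step 3: what the correct outcome would change (for scale only).** The inputs are from Section 15: 1000 European patients at 10% mutation frequency, 300 Japanese patients at 30%, and an assumed sensitivity of 50%.

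- The plan's own precision figure reproduces. For 50 of 100, the exact 95% CI is 39.8% to 60.2% and the Wald CI is 40.2% to 59.8%. Both round to the stated 40-60%.
- Tumour positives: 1000 × 0.10 + 300 × 0.30 = 100 + 90 = 190. Section 15 states 100 positives for Japan, but its own inputs give 90, and I use 90.
- Plasma-negative among tumour-positive at 50% sensitivity: 190 × (1 − 0.50) = 95. As a share of all patients: 95 / 1300 = 7.3%.
- Plasma positives, with no false positives: 190 × 0.40 = 76, 190 × 0.50 = 95, 190 × 0.60 = 114.
- Events per covariate, with eight single-parameter covariates: 76 / 8 = 9.5, 95 / 8 = 11.9, 114 / 8 = 14.25. The tumour model has 190 / 8 = 23.75.

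The corrected model can therefore be fitted, with about half the events of the tumour model. These figures count changed outcome values. They do not show how far any odds ratio would move.

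**The case against.** **The intent is obvious.** Objective 6, Table 4, the subsection heading and the first words of the sentence all point to plasma, so a competent analyst would probably notice what looks like carried-over text. That is fair, and it makes the damage of two identical tables a possibility rather than a forecast. It does not make the sentence right. The outcome is stated explicitly, so this is not a detail left to the SAP. An SAP that follows the protocol repeats the error, and one that corrects it departs from the protocol.

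**Objective 6 is still addressed.** A reader might infer from the wrong outcome that objective 6 is never analysed. The documents do not support that. The plasma subsection plans a summary of plasma status by demographic and disease characteristics and a comparison with the tumour summaries. The synopsis says that basic summary statistics are the means of meeting the objectives. What is missing is the adjusted analysis only.

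**The size is soft.** This stands too. The figure of 95 needs every patient to be evaluable and no plasma-positive, tumour-negative patients, although Section 14.1 plans to estimate specificity. The 50% is a planning value. Half of the tumour positives is also only about 7% of all patients. If missed plasma detection were unrelated to the covariates, the odds ratios of the two models could be similar.

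**The analysis is secondary and descriptive.** Section 12.1 rules out formal hypothesis tests. The concordance analysis and the sample size do not depend on this model.

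**Conclusion.** The point holds in a limited form. The plasma regression in Section 14.2 has the wrong dependent variable, contradicts objective 6 and Table 4, and duplicates the tumour regression. This follows from the text alone and rests on no numerical assumption.

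The consequence is that objective 6 has no valid multivariable analysis and keeps its descriptive one. It would go too far to say that the objective is unanswered, or that the published odds ratios would be wrong by any known amount.

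As an indication of scale, about 95 of 190 tumour-positive patients would change outcome value, and 76 to 114 at sensitivities of 60% down to 40%. This assumes full evaluability and no plasma false positives. Incomplete evaluability would lower the count, and false positives would raise it.

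**What to change.** In the plasma subsection of Section 14.2, replace the outcome of the regression with: EGFR plasma mutation status at baseline (EGFR mutation positive versus EGFR mutation negative from plasma sample). The population and covariates can stay as they are for this purpose. The cost is one phrase in a protocol amendment, with no new data and no change to the sample size.

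A second model could be added as an option: plasma positive yes or no among tumour-positive patients only, with the same covariates. It would separate plasma detection from tumour prevalence, which is close to the interest stated in the descriptive paragraph. Objective 6 does not require it, and curing the error does not need it. On the assumptions above it would rest on about 190 patients with 95 events, or about 12 per covariate.
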